4.3 Exclusion Criteria

- 4.3.1 History of CNS3 disease and/or active central nervous system (CNS) disease (\geq CNS2)
- 4.3.2 Receiving concomitant chemotherapy (with the exception of a tyrosine kinase inhibitor (e.g. imatinib, dasatinib, nilotinib) for Philadelphia-chromosome positive or Philadelphia-chromosome Like (Ph-Like) BALL), radiation therapy; immunotherapy or other anti-cancer therapy other than is specified in the protocol.
- 4.3.3 Systemic fungal, bacterial, viral, or other infection not controlled (defined as exhibiting ongoing signs/symptoms related to the infection and without improvement, despite appropriate antibiotics or other treatment)
- 4.3.4 Pregnant or lactating. The agents used in this study are known to be teratogenic to a fetus and there is no information on the excretion of agents into breast milk. All females of childbearing potential must have a blood test or urine study within 7-days prior to the start of blinatumomab to rule out pregnancy.
- 4.3.5 Known allergy to blinatumomab
- 4.3.6 Participating in a concomitant Phase 1 or 2 study

5.0 REGISTRATION PROCEDURES (STUDY ENTRY, STUDY PROCEDURES, END OF TREATMENT AND WITHDRAWL PROCEDURES)

Registration will occur after eligibility is confirmed and the patient/parent has signed the subject consent, but before any treatment has been administered. Questions regarding eligibility should be directed to the Principal Investigator: [name] ([contact]; email

[contact])

The eligibility checklist will be completed at the time of study enrollment.

5.1 Study Entry Procedures

5.1.1 Required Preregistration Screening Tests and Procedures

Screening assessments must be performed within 14-days prior to enrollment. Any results falling outside of the reference ranges may be repeated at the investigator's discretion. All on-study visit procedures are allowed a window of \pm 2 days unless otherwise noted. Treatment or visit delays for public holidays or weather conditions do not constitute a protocol violation.

A written, signed informed consent form (ICF) and a Health Insurance Portability and Accountability Act (HIPAA) authorization must be obtained before any study-specific assessments are initiated. A copy of the signed ICF and HIPAA form will be given to the subject and a copy will be filed in the medical record. The original will be kept on file with the study records.

All patients who are consented will be registered in the Online Enterprise Research Management Environment (OnCore™), the MCW Cancer Center and Pediatric Clinical Trials Office (CTO) Clinical Trial Management System. The system is password protected and meets HIPAA requirements.

5.1.2 Registration Process

Upon completion of the screening evaluation, eligibility confirmation and obtaining written consent, the patient will be registered in the study file by the Department of Pediatrics Division of Hematology/Oncology/BMT MACC Fund Center CTO).

5.1.3 Pretreatment Period

Screening Assessments: The screening procedures and assessments must be completed within 14-days of the Day 1 visit (or the first day of blinatumomab infusion).

- Physical examination
- Vital signs
- Complete medical history
- Baseline conditions assessment
- Documentation of disease assessment (disease-specific staging criteria)
- Performance status (ECOG, KPS, etc.)
- Measurable disease
 - Bone marrow aspirate and/or biopsy (morphology, cytogenetics, FISH and minimal residual disease (MRD) via HTS and flow cytometry). Baseline blast samples will be sent for B-cell and T-cell clonality HTS assessment, since B-lymphoblasts may have detectable T cell receptor (TCR) clones. If T-cell clonal sequences are detected on the baseline sample, T-cell clonality will continue to be sent along with B-cell clonality on subsequent samples (Note that prior MRD by HTS is required, but does not need to be completed within the 14 day window).

- Lumbar Puncture (CSF cytology and cell count)
- History of prior treatments and any residual toxicity relating to prior treatment
- Baseline medications taken within 14-days of Day 1
- Complete blood count (CBC) with differential and platelet count
- Blood chemistry assessment, including:
 - Alkaline phosphatase, aspartate aminotransferase/alanine aminotransferase (ALT/AST), total bilirubin, calcium, phosphorus, blood urea nitrogen (BUN), creatinine, total protein, albumin, glucose, potassium, sodium, chloride, bicarbonate, uric acid, lactate dehydrogenase (LDH).
- Coagulation assessment, including prothrombin time, partial thromboplastin time, international normalized ratio (PT/PTT/INR)
- Urinalysis
- Serum or urine pregnancy test (if applicable) within 7-days prior to the start of blinatumomab
- Electrocardiogram (EKG)
- Cardiac assessment (ECHO, MUGA, etc.)
- CMV serology and EBV serology prior to the start of the first cycle of blinatumomab

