4.2 Inclusion Criteria

4.2.1 Diagnosis of B-ALL in hematologic complete remission (defined as an M1 marrow, < 5% blasts) with MRD in the bone marrow ($\geq 0.01\%$) by multi-parameter flow cytometry and that meets one of the following:

- Patients in first relapse or greater;

OR

- Patients with very-high risk biology ALL that is proceeding to HCT in first remission (e.g. Induction failure, Severe-hypodiploidy, Ph-like ALL);

OR

- Patients who have persistent MRD after Consolidation therapy (End of Consolidation (EOC) MRD positive $\geq 0.01\%$);

AND with the intent of going on to an allogeneic hematopoietic cell transplantation (HCT) independent of this study

- 4.2.2 Patients must have an available donor and have intention of proceeding directly to HCT after completion of 1 to 2 cycles of Bridging therapy with blinatumomab.
- 4.2.3 Age \leq 25 years at time of study enrollment
- 4.2.4 Karnofsky Performance Status \geq 50% for patients 16 years and older and Lansky Play Score \geq 50 for patients under 16 years of age (see Appendix 1)
- 4.2.5 Have acceptable organ function as defined within 7 days of study registration:

Renal: creatinine clearance \geq 60 mL/min/1.73m² **or** serum creatinine based on age/gender as follows:

Age	Maximum Serum Creatinine (mg/dl)	
	Male	Female
1 month to < 6 months	0.4	0.4
6 months to < 1 year	0.5	0.5
1 year to < 2 years	0.6	0.6
2 years to < 6 years	0.8	0.8
6 years to < 10 years	1.0	1.0
10 years to < 13 years	1.2	1.2
13 years to < 16 years	1.5	1.4
\geq 16 years	1.7	1.4

Hepatic: ALT < 5 x upper limit of normal (ULN) and total bilirubin \leq 1.5 x upper limit of normal (ULN) for age

Cardiac: left ventricular ejection fraction \geq 40% by ECHO/MUGA

- 4.2.6 At least 7 days must have elapsed from prior chemotherapy.
- 4.2.7 Patients who have experienced their relapse after HCT are eligible, provided they have no evidence of acute or chronic Graft-versus-Host Disease (GVHD) and are off all transplant immune suppression therapy for at least 7-days (e.g. steroids, cyclosporine, tacrolimus). Steroid therapy for non-GVHD and/or non-leukemia therapy is acceptable.

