- 4.2.8 Biologic (anti-neoplastic agent): At least 7 days after the last dose of a biologic agent. For agents that have known adverse events occurring beyond 7 days after administration, this period must be extended beyond the time during which adverse events are known to occur. The duration of this interval must be discussed with the study chair. Patients with Philadelphia-chromosome positive or Philadelphia-chromosome like (PH-Like) BALL are an exception to this eligibility criteria as concomitant TKI therapy is allowed on study (e.g. imatinib, dasatinib, nilotinib).

- 4.2.9 Monoclonal antibodies: At least 3 half-lives of the antibody must have elapsed after the last dose of monoclonal antibody (i.e. Inotuzumab = 12 days).
- 4.2.10 Immunotherapy: At least 42 days after the completion of any type of immunotherapy (e.g. tumor vaccines or CAR T-cell therapy) **except monoclonal antibodies**.
- 4.2.11 XRT: Cranio or craniospinal XRT is prohibited during protocol therapy. ≥ 90 days must have elapsed if prior TBI, cranio or craniospinal XRT
- 4.2.12 Sexually active females of child-bearing potential must agree to use adequate contraception (diaphragm, birth control pills, injections, intrauterine device [IUD], surgical sterilization, subcutaneous implants, or abstinence, etc.) for the duration of treatment and for 2 months after the last dose of chemotherapy. Sexually active men must agree to use barrier contraceptive for the duration of treatment and for 2 months after the last dose of chemotherapy.
- 4.2.13 Voluntary written consent before performance of any study-related procedure not part of normal medical care, with the understanding that consent may be withdrawn by the subject at any time without prejudice to future medical care.

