5.2 Study Procedures During Treatment

Patients must meet eligibility criteria on Day 1 to be treated as per this protocol.

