6.2 Sample Collection and Processing for Minimal Residual Disease

Type of Sample	Instructions and Timing of Sample Collection
Bone Marrow Samples for Flow Cytometry MRD	
 At the end of each blinatumomab cycle (Day 28 \pm 2 days).
Bone Marrow Samples for Flow Cytometry MRD Bone Marrow Collection and Shipping Procedure	
 Bone marrow required for Flow Cytometry clinical evaluation MRD testing should be collected and shipped according to the standard procedures for the local institution. These samples will be evaluated by an approved Flow Cytometry Laboratory. Results of the clinical evaluation Flow Cytometry MRD testing at each timepoint will be communicated to each local institution by the approved Flow Cytometry Laboratory, and results should be entered into the EDC system by local Clinical Research Coordinators.
Bone Marrow Samples for High Throughput Sequencing MRD Samples	
 At time of enrollment prior to start of blinatumomab At the end of each blinatumomab cycle (Day 28 \pm 2 days). Baseline blast samples will be sent for B-cell and T-cell clonality assessment. If T-cell clonal sequences are detected on the baseline sample, T-cell clonality will continue to be sent along with B-cell clonality on subsequent samples. If no trackable T-cell sequences are detected, only B-cell HTS will be followed.

Type of Sample	Instructions and Timing of Sample Collection
Bone Marrow Sample for High Throughput Sequencing MRD Collection Procedure	
 Collect minimum of 2 mL of marrow into a syringe and place marrow into a large purple EDTA tube that are commonly used in all hospitals. Mix well Reposition marrow aspirates needle at least once during procedure to ensure the maximum quality of marrow
Specimen Labeling for High Throughput Sequencing MRD Sample	Each tube must be labeled with the study ID number, along with the date the sample was obtained. No personal identifying patient information should be included in the specimen or transmittal form.

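### The qualifying flow-MRD marrow may be drawn before the last dose of prior systemic therapy, so clearance by that earlier drug could be counted as a blinatumomab response

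*Combined protocol and SAP*

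**What the plan says.** All references are to the combined protocol and SAP.

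- **Marrow window.** Section 5.1.3, which lists the screening marrow with flow and HTS MRD: "The screening procedures and assessments must be completed within 14-days of the Day 1 visit (or the first day of blinatumomab infusion"). Section 5.1.1 uses a different anchor: "Screening assessments must be performed within 14-days prior to enrollment".
- **Washouts.** Section 4.2.6: "At least 7 days must have elapsed from prior chemotherapy". Section 4.2.8: "At least 7 days after the last dose of a biologic agent", with a longer interval for some agents and an exception for a TKI. Section 4.2.9: "At least 3 half-lives of the antibody must have elapsed after the last dose of monoclonal antibody (i.e. Inotuzumab = 12 days").
- **Day 1.** Section 5.2: "Patients must meet eligibility criteria on Day 1 to be treated as per this protocol". Neither the study calendar nor section 5.2.1 lists a marrow between baseline and the end of the cycle.
- **Endpoint and population.** Section 10.1.1 counts subjects who remain in CR and become flow-MRD negative after one or two cycles. Section 10.6 admits everyone with at least one course and an MRD assessment. Neither refers to the timing of prior therapy.
- **HTS.** Section 5.1.3 adds: "Note that prior MRD by HTS is required, but does not need to be completed within the 14 day window". Section 6.2 lists an HTS marrow sample "At time of enrollment prior to start of blinatumomab".

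**The concern.** The primary objective (section 2.2) attributes elimination of flow MRD to blinatumomab. With no control arm, that attribution rests on the baseline marrow showing the disease that blinatumomab then met. If a patient is found MRD positive, receives one more dose of chemotherapy or a biologic, and then starts blinatumomab, some or all of the later clearance may belong to the earlier drug. Section 4.3.2 excludes concomitant chemotherapy, not a dose given before Day 1 but after the marrow.

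The error runs in one direction. Carry-over can turn a blinatumomab non-responder into a counted responder and cannot do the reverse. What is at stake is the comparison with the 40% null rate and the R < 15 failure line in section 10.4.

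**Working it through.** **1. Calendar check.** Inputs: marrow up to 14 days before Day 1 (5.1.3); minimum washouts from 4.2.6 and 4.2.8 to 4.2.11. Longest time by which the marrow can precede the last dose = marrow window − washout:

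| Prior therapy | Washout (days) | 14 − washout |
|---|---|---|
| Chemotherapy | 7 | 7 |
| Biologic | at least 7 | at most 7 |
| Named antibody | 12 | 2 |
| Other immunotherapy | 42 | none |
| TBI or cranial radiotherapy | 90 | none |

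Example: marrow 14 days before Day 1 with MRD ≥ 0.01%, chemotherapy 8 days before Day 1, then blinatumomab. Every written timing rule is met. These are maxima. Section 4.2.6 gives no anchor for its 7 days. Counted back from Day 1, the gap can reach 7 days; counted back from an enrolment earlier than Day 1, it is shorter; counted back from the marrow, it disappears. The text does not say which is meant.

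**2. The plan's own operating characteristics.** Section 10.4 gives n = 12 then 25, null 0.40, alternative 0.67, cut-offs R ≤ 4 and R ≥ 10 at stage 1 and R < 15 at the end, type I error 0.0333 and power 0.8071. Treating R ≤ 4 as a stop:

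P(success | p) = P(X₁₂ ≥ 10) + Σ (x = 5 to 9) P(X₁₂ = x) · P(X₁₃ ≥ 15 − x)

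The printed cut-offs give 0.0350 at p = 0.40 and 0.8303 at p = 0.67, so the stated pair is not reproduced exactly. A stage 1 lower cut-off of 5 gives 0.0333 and 0.8152. That mismatch is a separate matter and hardly changes what follows.

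**3. Sensitivity to carry-over (assumed).** Let f be the share of blinatumomab non-responders cleared by a drug given after the baseline marrow. With a true blinatumomab rate of 0.40, the apparent rate is 0.40 + 0.60·f. Using the printed cut-offs:

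| f (assumed) | Apparent rate | P(success) |
|---|---|---|
| 0 | 0.40 | 0.035 |
| 5% | 0.43 | 0.066 |
| 10% | 0.46 | 0.115 |
| 20% | 0.52 | 0.276 |

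The probability passes 0.05 at f of about 3% (apparent rate about 0.416). Since f is the share of non-responders dosed after their marrow multiplied by the share of those whom the dose clears, f = 10% would need, for example, 20% dosed in the gap and half of them cleared (0.20 × 0.50). The documents give neither share.

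**4. Illustration in counts (also assumed).** If 13 of 25 clear because of blinatumomab (52%) and 3 more because of the earlier drug, the count is 16 of 25 (64%) and passes the R < 15 line. This needs 3 of the 12 non-responders (25%) to be cleared by carry-over, which is beyond the range tabulated above.

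**5. HTS.** The HTS endpoints in sections 10.1.2, 10.4 and 10.7.3.1 are proportions with undetectable HTS MRD after treatment. Section 10.7.1 collects HTS MRD at the end of each cycle. None of these uses a baseline HTS level.

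**The case against.** The strongest reply is section 5.2: if all criteria must hold on Day 1, so must MRD ≥ 0.01%, and the sequence above is already forbidden. Read literally, that is right. But no marrow is scheduled between the interposed dose and Day 1, so the criterion can be asserted but not checked. Confirmation of eligibility before enrolment (section 11.2) has the same limit, because it checks criteria that set no order. End-of-Consolidation MRD is measured after a completed course, but that does not exclude a further dose before Day 1.

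Other replies stand and narrow the point:

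- A reader might infer that carry-over can never be separated from the blinatumomab effect. Section 5.1.3 collects the history of prior treatments and all medications within 14 days of Day 1, so affected subjects can be identified.
- A reader might infer that an archival HTS sample biases the HTS results without limit. The documents do not support this. No planned HTS endpoint uses a baseline level, section 6.2 already lists an enrolment sample, and the waiver sits beside the text on clone identification. The reduction in burden in hypothesis 2.1 has no matching change-from-baseline endpoint.
- A reader might want all anti-leukemia therapy barred between marrow and Day 1. That would collide with section 1.2, which describes intrathecal chemotherapy before blinatumomab.
- Ordering the dates does not end carry-over: a marrow drawn the day after a dose complies, and later clearance from that dose still falls after baseline.

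**Conclusion.** The gap in the text is real: up to 7 days for systemic chemotherapy or a biologic and up to 2 days for the named antibody, provided the washout is counted back from Day 1. Nothing in the endpoint or analysis population removes a responder who passed through it, and any effect favours success. That calendar result is firm.

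The size of the bias is not known. The documents do not say how often a dose would follow the marrow or how many clearances it would cause. The probabilities from 0.035 to 0.276 and the 13-versus-16 example show how little carry-over the decision rule tolerates; they do not predict what will happen. It would go too far to say that the primary result will be inflated or that the HTS endpoints are biased. The point merits a change in wording and a sensitivity analysis; it does not call for a change in design.

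**What to change.** 1. In sections 4.2.1 and 5.1.3, state that the qualifying flow-MRD marrow is the screening marrow collected after the last dose of prior systemic anti-leukemia therapy. Say that the permitted TKI and the pre-blinatumomab intrathecal therapy described in section 1.2 fall outside this rule.
2. In section 10.7.2, for any subject whose marrow came first, report the primary proportion with and without that subject, using the prior-treatment and 14-day medication records already collected under section 5.1.3.
3. Give the 14-day windows in 5.1.1 and 5.1.3 and the washout in 4.2.6 explicit, consistent anchors.
4. For HTS, only reconcile the waiver in 5.1.3 with the enrolment sample in 6.2, stating what each sample is for.

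Cost: wording and one extra line in the analysis. Sample size, decision rule and washout lengths stay as they are. An occasional screening marrow must be timed later, or repeated if it was drawn before a further dose, and a patient who is MRD negative on the later marrow would not qualify. The ordering reduces carry-over without removing it, which is why the with-and-without report covers only subjects whose marrow came first and the remaining limitation should be stated with the result.

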5.2 Study Procedures During Treatment

Patients must meet eligibility criteria on Day 1 to be treated as per this protocol.

5.2.1 Study Procedures, Cycle 1 (and cycle 2, if applicable), Weekly

- Physical examination
- Vital signs
- Performance status
- Evaluation of adverse events
- Concomitant medications
- CBC with differential and platelet count
- Blood chemistry assessment, including:
 - Alkaline phosphatase, ALT/AST, total bilirubin, calcium, BUN, creatinine, total protein, albumin, glucose, potassium, sodium, chloride, bicarbonate,
- Coagulation assessment, including PT/PTT/INR (Day 1)
- Urinalysis, uric acid, LDH, phosphorus (Day 1)

5.3 End of Treatment

5.3.1 End of Treatment Procedures

To be completed on treatment Day 28 ± 2 days.

- Bone marrow aspirate and/or biopsy (morphology, cytogenetics, FISH and minimal residual disease via HTS and flow cytometry). Baseline blast samples will be sent for B-cell and T-cell clonality assessment. If T-cell clonal sequences are detected on the baseline sample, T-cell clonality will continue to be sent along with B-cell clonality on subsequent samples. If no trackable T-cell sequences are detected, only B-cell HTS will be followed.

- Lumbar puncture (CSF cytology and cell count)

5.4 Post-Treatment

5.4.1 Follow-Up Visits

All subjects, including those who discontinue protocol therapy early, will be followed for 30 days from the completion of blinatumomab or until the start of the transplant preparative regimen (or other therapy), whichever occurs earlier.

The following procedures will be performed at the follow-up visit(s): Weekly

- Physical examination
- Vital signs
- Performance status
- Evaluation of adverse events
- Concomitant medications
- CBC with differential and platelet count
- Blood chemistry assessment, including:
 - Alkaline phosphatase, ALT/AST, total bilirubin, calcium, BUN, creatinine, total protein, albumin, glucose, potassium, sodium, chloride, bicarbonate,

5.5 Study Withdrawal Procedures

5.5.1 Duration of Therapy

Treatment will be limited to 1 to 2 cycles of blinatumomab. An additional cycle of Blinatumomab bridging therapy can be given if needed based on timing of donor collection. This additional cycle for subjects awaiting donor collection, may be 28 days but can be less if the HCT is ready to proceed (e.g. 14-day blinatumomab infusion). Subjects will receive protocol therapy unless:

- Subject withdraws consent or is non-compliant
- Disease progression
- Inter-current illness that prevents further administration of treatment
- Unacceptable toxicity

5.5.2 Subject-Initiated Withdrawal

A subject may decide to withdraw from the study at any time.

5.5.3 Investigator-Initiated Withdrawal

The Investigator will withdraw a patient whenever continued participation is no longer in the patient's best interests. Reasons for withdrawing a patient include, but are not limited to, disease progression, the occurrence of an adverse event or a concurrent illness, a subject's request to end participation, a subject's noncompliance or simply significant uncertainty on the part of the Investigator that continued participation is prudent. There may also be administrative reasons to terminate participation, such as concern about a subject's compliance with the prescribed treatment regimen.

5.5.4 Sponsor-Initiated Withdrawal

Sponsor's decision to discontinue the study.

5.5.5 Withdrawal Documentation Procedure

The reason for study withdrawal and the date the subject was removed from the study must be documented in the case report form (CRF). As this study will enroll up to 35 patients in order to capture 25 evaluable subjects, it will account for subjects that may withdraw from study. Any subject who receives any amount of blinatumomab will be evaluable for toxicity and followed until they either come off study or begin a new treatment for their leukemia, which would include HCT.

5.5.6 Off Study Criteria

- Death
- Lost to follow-up
- Patient enrollment onto another anti-cancer therapeutic study **with exception to Part 2 of this study**
- Withdrawal of consent for any further data submission
- Protocol defined follow up criteria met

